1.2. The War-Drill Model and Sine Qua Non Hypothesis Nimsai Academia proposes a paradigm shift in understanding HD through the "War-Drill Model." This model posits that venous congestion, rather than primary venous dilatation, is the fundamental and indispensable prerequisite (Sine Qua Non Hypothesis) for the development and progression of hemorrhoidal disease. This congestion leads to secondary vascular deformation and the manifest symptoms. The model categorizes HD into two distinct modes:

- **War Mode Hemorrhoids:** Characterized by chronic venous congestion often driven by systemic or local inflammatory conditions (inflammatory bowel disease, anal fissures, liver cirrhosis, chronic constipation). These hemorrhoids may serve as an early biological warning system for up to 20 potential underlying pathologies, necessitating a comprehensive diagnostic workup and systemic therapeutic intervention.
- **Drill Mode Hemorrhoids:** Characterized by transient vascular engorgement primarily due to hormonal fluctuations (pregnancy, menopause). These are typically self-limiting and may resolve spontaneously once the hormonal influence subsides. The "Parola Phenomenon," a clinical maneuver developed by Nimsai Academia, is hypothesized to differentiate between War Mode and Drill Mode hemorrhoids with high sensitivity and specificity (reported 94% sensitivity and 91% specificity), thereby guiding appropriate diagnostic and therapeutic strategies.

1.3. Rationale for Nimsai Herbal Intervention Nimsai Herbal is a proprietary botanical formulation specifically designed to target the underlying venous congestion proposed by the War-Drill Model. Its active components – *Centella asiatica* extract, *Curcuma longa* extract, and *Piper nigrum* extract – are selected for their venotonic, anti-inflammatory, antioxidant, and

bioavailability-enhancing properties. By addressing the root cause of venous congestion, Nimsai Herbal is hypothesized to offer a more effective and sustainable treatment approach compared to symptomatic or localized therapies. The systemic nature of Nimsai Herbal aligns with the War-Drill Model's emphasis on underlying systemic or local inflammatory conditions contributing to hemorrhoidal pathogenesis.

1.4. Study Rationale and Justification This randomized controlled trial (RCT) is designed to rigorously evaluate the efficacy and safety of Nimsai Herbal in patients with Grade 2-3 hemorrhoids. The study will not only assess the clinical benefits of Nimsai Herbal but also provide further clinical validation for the War-Drill Model and its implications for diagnosis and treatment. Establishing the efficacy and safety of Nimsai Herbal could lead to a significant improvement in patient care, reduce recurrence rates, and potentially yield substantial global healthcare savings by facilitating early diagnosis of underlying conditions and reducing the need for invasive procedures.

2. Study Objectives

2.1. Primary Objective To evaluate the efficacy of Nimsai Herbal capsules in achieving hemorrhoid regression, defined as a $\geq 75\%$ reduction in composite hemorrhoid severity score from baseline to Day 10, compared to placebo in patients aged 18-70 years with symptomatic Grade 2-3 internal hemorrhoids.

2.2. Secondary Objectives

- To assess the mean change in self-reported hemorrhoid symptom severity using a Visual Analog Scale (VAS) from baseline to Day 10.
- To determine the percentage of participants achieving complete resolution of baseline hemorrhoid symptoms (composite severity score = 0) by Day 10.
- To explore the clinical utility of the War-Drill Model in guiding treatment response and diagnostic pathways.
- To evaluate the proportion of participants experiencing a significant reduction in individual symptoms (bleeding, pain, itching, swelling) by Day 10.

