7.2.3. Reduction in Individual Symptom Scores

- Name: Mean Reduction in Individual Symptom Scores (Bleeding, Pain, Itching, Swelling)
- Definition: Mean change from baseline to Day 10 for each individual symptom (bleeding, pain, itching, swelling) as assessed by the investigator using the 0-10 scale.
- Time Frame: Baseline to Day 10.
- Unit of Measure: Score (0-10 scale).
- Assessment Method: Clinician assessment via CRFs.

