10.5. Secondary Outcome Analysis

- **VAS Symptom Score Change:** The mean change from baseline will be compared between groups using a Mann-Whitney U test due to potential non-normal distribution of symptom scores. The effect size will be reported as a Mean Difference with 95% CI. Baseline VAS scores may be included as a covariate in sensitivity analyses (ANCOVA).
- **Symptom Resolution Rate:** Compared between groups using a Chi-square test. The effect size will be reported as a Risk Ratio with 95% CI. Logistic regression may be used to adjust for baseline severity.
- **Individual Symptom Scores:** Mean changes will be compared using appropriate parametric (t-test) or non-parametric (Mann-Whitney U) tests based on data distribution.

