- **Interim Analysis:** No interim analyses are planned for this study, given its short duration (10 days) and the low expected risk of serious adverse events (SAEs).

3. Outcome Measures and Statistical Analysis

This section details the statistical methods for each predefined outcome measure.

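### A secondary objective asks for the proportion with a reduction in each symptom, but the outcome and analysis give only mean changes and the SAP has no entry for it

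*Protocol*

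**What the plan says.** - **Objective (Protocol 2.2):** "To evaluate the proportion of participants experiencing a significant reduction in individual symptoms (bleeding, pain, itching, swelling) by Day 10". This is a percentage of people, and it needs a rule for who counts as improved.
- **Outcome (Protocol 7.2.3):** named "Mean Reduction in Individual Symptom Scores (Bleeding, Pain, Itching, Swelling)" and defined as "Mean change from baseline to Day 10 for each individual symptom (bleeding, pain, itching, swelling) as assessed by the investigator using the 0-10 scale". The unit is given as "Unit of Measure: Score (0-10 scale)".
- **Analysis (Protocol 10.5):** "Mean changes will be compared using appropriate parametric (t-test) or non-parametric (Mann-Whitney U) tests based on data distribution". Unlike the lines for VAS change and symptom resolution in the same section, this one names no effect measure and no confidence interval.
- **SAP section 3:** opens with "This section details the statistical methods for each predefined outcome measure". Its secondary outcomes are VAS change (3.2.1) and symptom resolution (3.2.2). Individual symptoms do not appear.
- **The only partial-response threshold in either document:** the 75% rule in Protocol 2.1 and 7.1 and SAP 3.1, which applies to the 0-40 composite: "reduction in composite hemorrhoid severity score from baseline to Day 10, compared to placebo".

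**The concern.** An objective should lead to an outcome, and the outcome to an analysis. Here the objective is a responder proportion, while the outcome and analysis are a mean difference on a 0-10 scale. A statistician who follows the plan exactly will have nothing to report against this objective. Anyone who later wants to report on it must supply a cut-off for each of four symptoms, and if that is done after the data are seen, the choice can shape the answer. The SAP is where such a gap would normally be closed, but it leaves the individual symptoms out.

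**Working it through.** **1. The plan's own design figure.** The one design figure stated is the primary comparison: 150 per arm, 50% versus 20%, two-sided alpha 0.05, power above 90% (Protocol 3.3, SAP 3.1).

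- Pooled proportion: (0.50 + 0.20)/2 = 0.35.
- Standard error under no difference: √(2 × 0.35 × 0.65/150) = 0.0551.
- Standard error under the assumed difference: √((0.50 × 0.50 + 0.20 × 0.80)/150) = 0.0523.
- Power: Φ((0.30 − 1.96 × 0.0551)/0.0523) = Φ(3.67) = 0.9999.

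The stated figure holds, and the point made here does not bear on it.

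**2. The objective against each place that might answer it.**

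| Place | Quantity | Proportion per symptom? |
|---|---|---|
| Protocol 2.2 | Proportion with a significant reduction, per symptom | Asked for; no threshold |
| Protocol 7.2.3 | Mean change, score units | No |
| Protocol 10.5, individual symptoms | t-test or Mann-Whitney U on changes | No |
| Protocol 7.1, SAP 3.1 | Proportion with at least 75% reduction | Composite only |
| Protocol 7.2.2, SAP 3.2.2 | Proportion with composite equal to 0 | No; all four symptoms must be absent together |
| SAP 3.2 | VAS change, symptom resolution | No individual-symptom entry |

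Nothing in the last five rows delivers the first.

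**3. Can the mean change stand in for the proportion?** The documents give no means or SDs for symptom changes, so this is an illustration on assumed values: normally distributed reductions with mean 3 points and SD 1, 2 or 3. The share improving by at least t points is 1 − Φ((t − 3)/SD).

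| Threshold t | SD 1 | SD 2 | SD 3 |
|---|---|---|---|
| 2 points | 84.1% | 69.1% | 63.1% |
| 4 points | 15.9% | 30.9% | 36.9% |
| 5 points | 2.3% | 15.9% | 25.2% |

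The mean is the same in every cell, yet the proportion runs from 2.3% to 84.1%. Two arms with equal means and SDs of 1 and 3 would differ by 84.1 − 63.1 = 21.0 percentage points in favour of the first at a 2-point threshold, and by 36.9 − 15.9 = 21.0 points in favour of the second at 4 points. So the mean does not determine the proportion, and the choice of threshold can even reverse the direction.

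**4. Are the data there?** Yes. Protocol 7.1 builds the composite from four clinician-rated items of 0-10, and Protocol 8.2 schedules it at Day 0 and Day 10. Either a mean change or a proportion can be computed; only the definition is missing.

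**The case against.** The strongest reply is that the clinical question is still addressed. The same four symptoms, scored by the clinician, are compared between arms at Day 10, and following the plan requires no cut-off. On this view the fault is one loosely worded bullet. Much of that stands: it is why rewording 2.2 is the simplest repair, and why a data-driven threshold is a risk and not a certainty. It does not remove the contradiction, because the objective still asks for a quantity that the plan never produces, and the SAP does not carry even the mean-change analysis.

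A reader might infer two stronger points, neither of which the documents support.

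- **That the mean over all participants is wrong because it dilutes the effect.** Protocol 4.1 requires no particular symptom, so some participants may score 0 on an item at baseline and have no room to improve. But the documents give no baseline symptom frequencies and no expected effect on any item, so the size of any dilution cannot be derived. The mean over all randomised participants is also a valid estimand: those starting at 0 can worsen, and it counts them.
- **That the plan already holds a threshold, namely 75%.** It is defined only for the 0-40 composite. On a single item it is a choice. If items are scored in whole points (not stated), a baseline of 1, 2 or 3 would have to reach 0 to qualify, so reduction would mean complete resolution for those participants.

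**Conclusion.** The point holds as a mismatch between objective, outcome and analysis, together with an omission from the SAP. It rests on the text alone; the illustration only shows why a mean cannot substitute for a proportion, and its mean and SDs are assumptions. The reach is small: one secondary objective, with the primary endpoint, its power and the other secondary outcomes untouched. It should not be read as saying that the mean-change analysis is invalid or that the individual symptoms go unexamined, since Protocol 10.5 does compare them. It is a minor point, worth correcting because the correction is nearly free.

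**What to change.** Make Protocol 2.2, 7.2.3 and 10.5 and a new SAP 3.2.3 name the same quantity.

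**Simplest option.** Reword 2.2 to the mean change from baseline to Day 10 in each of the four symptoms. In 10.5 and SAP 3.2.3, analyse each change with adjustment for that symptom's baseline score, which is already collected, and report a mean difference with 95% CI. This introduces no new cut-off. The cost is a few lines of text.

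**If the proportion is wanted.** Define one per-symptom responder threshold before unblinding; the composite's 75% is one candidate. Apply it at Day 10 to participants with a baseline score above 0 for that symptom, because a percentage reduction is undefined at 0. Report a risk difference with 95% CI. Restricting on a pre-treatment score keeps the randomised comparison. The costs are smaller denominators for each symptom, no count of symptoms that appear during treatment and, if the mean change is kept alongside, eight symptom comparisons in place of four.

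**Timing.** Protocol 3.2 ends the study period on November 14, 2021, and the Protocol's reference list includes a 2025 item, so data may already exist. If they have been seen, any threshold added now should be labelled post hoc.

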2.3. Safety Objectives

- To determine the incidence of mild gastrointestinal discomfort (nausea, bloating, dyspepsia) in both treatment groups during the 10-day intervention.
- To assess the incidence of Serious Adverse Events (SAEs) in both treatment groups during the 10-day intervention.
- To determine the incidence of participant withdrawals due to adverse events in both treatment groups during the 10-day intervention.
- To specifically monitor and report the incidence of transient diarrhea in diabetic participants during the first three days of the intervention.

3. Study Design

3.1. Overall Design This is a prospective, randomized, double-blind, placebo-controlled, parallel-group clinical trial. Participants aged 18-70 years with symptomatic Grade 2-3 internal hemorrhoids will be randomized in a 1:1 ratio to either the Nimsai Herbal group or the placebo group. The intervention period will be 10 consecutive days.

[figure not shown]
3.2. Study Period and Duration

- Overall Study Period: October 10, 2021, to November 14, 2021. This period includes participant screening, enrollment, 10-day intervention, and final data collection.
- Intervention Duration: 10 days for each participant.
- Total Study Duration per Participant: Approximately 10-14 days (including screening and final assessment).

3.3. Enrollment and Sample Size

- Planned Enrollment: A total of 300 participants will be enrolled (150 in the Nimsai Herbal group and 150 in the placebo group).
- Sample Size Justification: A sample size of 150 participants per arm (total 300) provides >90% power to detect a 30% difference in hemorrhoid regression rate (assuming 50% regression in the Nimsai Herbal group vs. 20% in the placebo group) with a two-sided alpha level of 0.05. This calculation accounts for potential minor dropouts.

3.4. Study Flow Diagram

4. Study Population

4.1. Inclusion Criteria Participants must meet all of the following criteria to be eligible for enrollment:

- Males and females aged 18 to 70 years, inclusive, at the time of signing the Informed Consent Form (ICF).
- Diagnosis of symptomatic internal hemorrhoids, clinically and endoscopically confirmed as Grade 2 or 3 according to the Goligher classification system.
- History of hemorrhoidal symptoms (e.g., bleeding, pain, itching, swelling, discomfort) persisting for more than 6 weeks prior to screening.
- Willingness and ability to provide written informed consent.
- Willingness and ability to comply with all study procedures, schedules, and follow-up requirements.
- Able to understand and communicate effectively in the local language of the study site.

4.2. Exclusion Criteria Participants will be excluded if they meet any of the following criteria:

- Diagnosis of Grade 1 or Grade 4 hemorrhoids.
- Any known anorectal malignancy or suspicion of malignancy (colorectal cancer, anal canal carcinoma, inflammatory bowel disease affecting the anorectum, severe anal fissures or fistulas requiring immediate surgical intervention).
- Active bleeding from sources other than hemorrhoids (diverticulitis, inflammatory bowel disease).
- Currently pregnant or lactating women, or women of childbearing potential not using an effective method of contraception.
- Known hypersensitivity or allergy to any component of Nimsai Herbal capsules or placebo ingredients.
- Significant systemic diseases including, but not limited to, severe cardiovascular disease (unstable angina, recent myocardial infarction), severe renal impairment (end-stage renal disease), severe hepatic dysfunction (decompensated cirrhosis), or uncontrolled diabetes mellitus (HbA1c > 9%).
- Any medical or psychiatric condition that, in the opinion of the investigator, might compromise the participant's safety, ability to complete the study, or the integrity of the study data.
- Participation in another interventional clinical trial within 30 days prior to screening or during the current study.
- Use of concurrent treatments for hemorrhoids (other oral supplements, topical creams, suppositories) within 7 days prior to screening or during the study period.
- History of hemorrhoidectomy or other invasive hemorrhoid procedures (banding, sclerotherapy) within the last 6 months.

4.3. Participant Recruitment Participants will be recruited through local advertising (posters in clinics, online advertisements, local media) at Nimsai Academia, Türkiye. All recruitment materials will be reviewed and approved by the Nimsai Academia Ethics Committee. Potential participants will undergo a preliminary phone screening to assess initial eligibility before scheduling an in-person screening visit.

4.4. Screening and Enrollment Procedures

- Screening Visit (Day -2 to Day 0):
 - Review of inclusion/exclusion criteria.
 - Detailed medical history including current and past medications.
 - Physical examination including digital rectal examination and anoscopy/endoscopy to confirm hemorrhoid grade.
 - Baseline assessment of hemorrhoid symptoms using a composite severity score (0-40) and VAS (0-10).
 - Collection of demographic data (age, sex).
 - Laboratory tests (complete blood count, liver and kidney function tests, fasting glucose/HbA1c for diabetic participants) to rule out underlying conditions as per exclusion criteria.
 - Informed consent process (detailed in Section 12.2).
- Enrollment (Day 0):
 - Participants meeting all inclusion and no exclusion criteria and who have provided informed consent will be officially enrolled.
 - Baseline data captured in CRFs and participant diary initiated.
 - Randomization will occur on Day 0.

5. Study Intervention

5.1. Nimsai Herbal Capsules (Active Arm)

- Formulation: Each Nimsai Herbal capsule contains 600 mg of a proprietary blend of standardized extracts: *Centella asiatica*, *Curcuma longa*, and *Piper nigrum*. The capsules are formulated for consistent potency, purity, and bioavailability, and manufactured under strict Good Manufacturing Practice (GMP) conditions.
- Dosage and Administration: One (1) Nimsai Herbal capsule (600 mg) will be administered orally, once daily, with water, preferably at a consistent time each day (morning).
- Packaging: Identical in appearance, size, color, and packaging to the placebo capsules to maintain blinding.

5.2. Placebo Capsules (Control Arm)

- Formulation: Each placebo capsule contains inert ingredients (microcrystalline cellulose, starch, coloring agents) and is devoid of any active pharmacological properties.
- Dosage and Administration: One (1) placebo capsule will be administered orally, once daily, with water, preferably at a consistent time each day.
- Packaging: Identical to the Nimsai Herbal capsules in appearance, size, color, and packaging to ensure effective blinding.

5.3. Administration Schedule and Adherence Monitoring

- Participants in both arms will receive their assigned study capsules sufficient for 10 days of treatment.
- Adherence Monitoring:
 - Daily Participant Diaries: Participants will record daily administration of the study capsule in their provided diary.
 - Pill Counts: At the end of the 10-day intervention (Day 10), remaining capsules will be counted to objectively assess adherence.
 - Investigator Inquiry: Investigators will periodically inquire about adherence during scheduled follow-up visits.
- Non-adherence (missing more than 2 doses) will be documented as a protocol deviation, but participants will remain in the Intention-to-Treat (ITT) analysis.

5.4. Concomitant Medications and Prohibited Therapies

- Participants will be instructed to avoid any other medications or therapies for hemorrhoids (oral, topical, or invasive procedures) during the study period.
- A list of all concomitant medications (prescription, over-the-counter, herbal supplements) will be recorded at screening and monitored throughout the study. Use of medications deemed essential for pre-existing conditions (antihypertensives, antidiabetics) will be permitted and documented.
- Prohibited therapies will include other venotonics, systemic anti-inflammatory drugs specifically for hemorrhoids, and any new laxatives or stool softeners unless medically necessary and documented.

6. Randomization and Blinding

6.1. Randomization Procedure

- Eligible participants will be randomized in a 1:1 ratio to either the Nimsai Herbal group or the placebo group.
- A computer-generated randomization sequence will be prepared by an independent third party (a contract research organization or a statistician not involved in study conduct) prior to the start of the study.
- The randomization sequence will be stratified by hemorrhoid severity (Grade 2 vs. Grade 3) to ensure an even distribution of severity across treatment arms.
- Study medication kits will be pre-packaged and labeled with unique randomization numbers. Once a participant is enrolled, the next sequential randomization number will be assigned.

6.2. Blinding Method This study will employ a quadruple-blind design, meaning the participant, the care provider, the investigator, and the outcomes assessor will all be blinded to the treatment assignment.

- Product Appearance: Nimsai Herbal and placebo capsules are identical in appearance, color, taste, and packaging.
- Packaging and Labeling: Study medication will be packaged in identical, opaque containers with only the randomization number and essential safety information displayed.
- Allocation Concealment: The randomization list will be securely maintained by the independent third party and will not be accessible to study personnel or participants.

6.3. Unblinding Procedures

- Emergency Unblinding: In the event of a medical emergency where knowledge of the assigned treatment is absolutely necessary for the participant's care (severe adverse reaction suspected to be related to the study product), emergency unblinding may occur. This will be performed by authorized personnel (unblinded pharmacist or designated study staff) following a pre-defined procedure. The reason for unblinding and the time/date will be thoroughly documented.
- Planned Unblinding: The full unblinding of the study results will only occur after the completion of all data collection, database lock, and final statistical analyses have been performed. An unblinded statistician, not involved in interim analyses or study conduct, will have access to the unblinded data for final analysis.

7. Outcome Measures

7.1. Primary Outcome Measure

- Name: Hemorrhoid Regression Rate
- Definition: The percentage of participants achieving a clinical response, defined as a $\geq 75\%$ reduction in their composite hemorrhoid severity score from baseline to Day 10. The composite score is derived from the sum of clinician-assessed scores for four key symptoms: bleeding, pain, itching, and swelling. Each symptom is rated on a 0-10 scale (0 = no symptom, 10 = most severe symptom), resulting in a total possible score range of 0-40.
- Time Frame: Measured at Day 10, representing the end of the intervention period.
- Unit of Measure: Percentage of Participants.

Assessment Method: Clinician assessment by blinded investigators using standardized Case Report Forms (CRFs). Investigator training will include calibration exercises to ensure consistent scoring at Nimsai Academia.

